9.5.2. Interim Analysis of Safety Data

Interim analysis may be conducted as recommended by the DSMB, to review safety data, including metabolic, immunological assessments and adverse events. The DSMB may recommend early stopping if there is sufficient evidence to conclude that the investigational treatment is harmful based on interim analysis of safety endpoints.

At any time, if there are significantly more adverse events in the experimental arm based on Fisher's exact tests for comparison, early termination should be considered. For example, a scenario where 9 patients have enrolled with 6 in the combination treatment arm and 3 in the vitamin D alone arm with 5 adverse events in the combination treatment arm and 0 in the vitamin D treatment arm would be considered significantly increased likelihood of adverse events in the combination treatment arm and would potentially result in trial termination. The same holds in the scenario where 15 patients have been enrolled with 10 in the combination treatment arm and 5 in the vitamin D alone treatment arm, where the combination treatment group experiences 9 adverse events while the vitamin D group experiences only 1. Similar scenarios exist throughout the trial and at any time if the exact test comparing groups under the null that the likelihood of adverse events is equal between groups exceeds a significance threshold of 0.05, this would warrant early termination.

9.5.3. Futility Analysis

Futility is unlikely to be shown during a one year treatment period, but the DSMB can decide to terminate the study should futility be shown. We do not intend to stop the study for futility as we intend to obtain an estimate and 95% confidence interval for the effect of treatment between groups at the 1 year mark

using the full information offered by our design. Additionally, not stopping for futility incorporates the consideration that the C-peptide AUC curves of combination therapy and vitamin D alone groups may separate later on follow-up, as AUC values decline further in the vitamin D alone group. Essentially all type 1 diabetes trials have been allowed to reach their one-year endpoint, even those that showed no efficacy.

9.6. Statistical Hypotheses

Primary hypothesis:

- Null: Patients receiving combination supplement therapy and patients in the Vitamin-D alone group have comparable proportions with maintained or increased C-peptide production, assessed by the measurement of the stimulated 90-minute C-peptide at one year of follow up.
- Alternative: Patients receiving combination therapy have higher proportions with maintained or increased C-peptide production, assessed by the measurement of the stimulated 90-minute C-peptide as compared to the proportion of patients with maintained or increased C-Peptide in the vitamin D alone group at one year of follow up.

9.7. Sample Size Considerations

Metabolic primary outcome

Sample size considerations correspond to the primary hypothesis which is that the proportion of patients with maintained or increased 90-min C-peptide at 12 months compared to baseline value is greater in the combination therapy group than in the vitamin D alone group. Standard power calculations for two sample tests of proportions indicate that 12 subjects in each group are needed to achieve 80% power to detect differences between less than 5% in the vitamin D alone group and at least 50% in the combination therapy group. Allowing for 10% dropout/attrition, sample size considerations include an allowance for 10% of the subjects to have missing data (one-year MMTT was not done or subject withdrew prior to the one-year assessment).

Primary endpoints should be available for all enrolled subjects. An exception will be if a death occurs or if the subject withdraws consent to be followed, although we expect this to be very limited. We also have included consideration for attrition in our design. Should there be any missing data, missing data will be assessed for mechanism of missingness and to see if missing at random assumptions are valid. If necessary, appropriate imputation strategies can be applied for sensitivity analysis. We will explore the data to assess if missingness at a given time point is related to observed data at the previous time point. If we find that, conditional on treatment group, observed values strongly predict subsequent values where observed, but are not related to missingness at subsequent time points, we may regard the missing data as a random sample of previously observed data.

10. ETHICAL CONSIDERATIONS & COMPLIANCE WITH GOOD CLINICAL PRACTICE

10.1. Statement of Compliance

The study will be conducted in accordance with the protocol, Good Clinical Practices, the relevant ICH guidelines, the applicable regulatory requirements, and the ethical principles that have their origins in the Declaration of Helsinki. As required by United States Food and Drug Administration (FDA) Code of Federal Regulations (CFR) (21 CFR 56) and the Declaration of Helsinki, the study protocol, amendments, and Informed Consent form will be reviewed and approved, according to 21 CFR §50 and §56, respectively, by University of Miami's IRB. Any amendments to the protocol or consent materials must also be approved before they are implemented.

10.2. Informed Consent

The consent process will be conducted by qualified study personnel (the Study Coordinator and/or Investigator or other designee). All participants (or their legally acceptable representative) must read, sign and date a consent or assent form prior to participation in the study, and/or undergoing any study-specific procedures.

The informed consent form must be updated or revised whenever there is new clinically significant information applicable to the safety of the participants when indicated for a protocol amendment, and/or whenever any new information becomes available that may affect a patient's participation in the study.

10.3. Study Subject Confidentiality

The investigational site participating in this study will maintain the highest degree of confidentiality permitted for the clinical and research information obtained from subjects. As a part of the quality assurance and legal responsibilities of an investigation, the investigational site must permit authorized representatives of the Quality Assurance division of University of Miami and regulatory agencies to examine (and when required by applicable law, to copy) records for the purposes of quality assurance reviews, audits and evaluation of the study safety and progress. Unless required by the laws permitting copying of records, only the coded identity associated with documents or other participant data may be copied (obscuring any personally identifying information). Authorized representatives, as noted above, are bound to maintain the strict confidentiality of medical and research information that may be linked to identify individuals. The investigational site will normally be notified in advance of auditing visits. Study records with the study subject's information for internal use at the clinical site will be secured at the study site during the study. At the end of the study, all records will continue to be kept in a secure location. There are no plans to destroy the records.

Study subject data, which is for reporting purposes, will be stored at the Diabetes Research Institute. Case report forms will identify participants by the unique Identification Number. At the end of the study, all study databases will be archived at the Center, and the data collection forms will be saved for long-term storage.

Stored samples including genetic samples could be utilized to learn more about causes of type 1 diabetes, its complications (such as eye, nerve, and kidney damage) and other conditions for which

individuals with diabetes are at increased risk, and how to improve treatment. The results of these future analyses, and any mechanistic studies will not be made known to the participant.

11. STUDY ADMINISTRATION

This study is investigator initiated study sponsored by the investigators from Diabetes Research Institute. Funding will cover the costs of administration and laboratory tests associated with this study during the participant's period of follow-up and procedures related to drug administration. Study drugs will be free of charge for the participant's entire length of treatment.

Since dosage of study drugs is dependent on blood levels (i.e., 25OH vitamin D and AA/EPA ratio) and results may take up to 1 week to be ready following blood collection during the participants' visits, participants who live far from the study site and logically cannot come to the site to pick-up their study drug outside of their scheduled study visit windows, may have the study drugs shipped to them. Both study drugs, vitamin D and omega 3 fatty acids, are stable at room temperature and do not require additional special handling during shipment except for adequate packing of the omega 3 bottles to ensure they do not break during transportation.

11.1. Groups and Committees

11.1.1. Protocol Development Committee

As acknowledged on the preface of this study protocol, protocol development committee met periodically over four months to finalize this protocol. Members of this committee bring interdisciplinary and translational expertise in pediatrics, immunology, transplantation and endocrinology of T1D, research nurse, research pharmacist and regulatory experts. Committee consists of Subject Matter Experts with unique and proven expertise in different immune pathways involved in T1D.

11.1.2. Clinical Site

The study will be conducted at Diabetes Research Institute and Mailman Center for Child Development. Principal Investigators of the participating clinical site will oversee all operations. The clinical sites will conduct the trial and collect all laboratory and data collection form information for analysis. Clinical research team meets every Friday of the week to discuss development and issues related to all clinical research studies at the institute and facilitate evaluation of the trial management.

11.1.3. Medical Monitor for the Clinical Protocol

This trial includes the medical monitor independent of the study ([name]., Professor of Surgery at the University of Miami Miller School of Medicine).

11.1.4. Clinical Site Monitoring

In order to conduct this study consistent with established research principles and ICH-GCP guidelines, there will be site visits conducted during the study to evaluate study conduct. Clinical Research Operation and Regulatory Support (CRORS) is part of the Research, Research Education & Innovative Medicine (RIM) Department, within the Miller School of Medicine at the University of Miami. The CRORS is independent of the Diabetes Research Institute and will provide source data verification and periodic monitoring for patient enrollment, compliance with protocol procedures, completeness and accuracy of data entered on the case report forms (CRFs), and the occurrence and reporting of adverse events (AEs) and serious adverse events (SAEs). The site will be monitored by the Clinical Research Associates from the CRORS.

11.1.5. Data and Safety Monitoring Board (DSMB)

The members of the DSMB are independent and serve in an individual capacity to provide their expertise and recommendations. They will review the 90 day data of the first 24 subjects, and then periodically review as per the charter and evaluate the accumulated study data for participant safety, study conduct and progress, and, when appropriate, efficacy, and make recommendations to study investigators concerning the continuation, modification, or termination of the trial. The DSMB members are experts in the field of T1D immunotherapy and will consider study-specific data as well as relevant background knowledge about the disease, test agents, and patient population under study. All adverse events will be recorded on the adverse event forms, which will be provided to the local IRBs, per their reporting requirements. The DSMB will independently evaluate whether the adverse events constitute grounds to discontinue the study.

11.1.6. DRI Office of Regulatory Support

This office of Quality Assurance and Regulatory Affairs provides standardized auditing functions, educational training, and regulatory support for clinical research at the Diabetes Research Institute.

11.1.7. Human Subjects Research Office & Institutional Review Boards (HSRO & IRB)

The HSRO provides administrative support for the University of Miami IRBs, which review proposed research involving human subjects to ensure the protection of those subjects and regulatory compliance.

11.1.8. Clinical Research Centers

Pediatric endocrinology clinics at the Mailman Center for Child Development and adult endocrinology clinics at Diabetes Research Institute and Clinical Translational Research Site at the University of Miami Miller School of Medicine provide comfortable, safe and effective environment to conduct professional, high-quality research involving human subjects.

11.1.9. Investigational Drug Services (Research Pharmacy)

The Investigational Drug Service (IDS) was established to provide pharmacy support to investigators in managing randomized, clinical trials at the University of Miami. The IDS also has the capability to dispensing complex investigational therapies and as drug safety experts therein can provide customized value that is increasingly recognized as a mechanism for assuring safety of study patients, ensuring adherence to protocol guidelines, and minimizing the liability associated in conducting drugs or supplement trials.

11.1.10. Core Laboratories

Core laboratories participating in the study include:

- Clinical research laboratories routinely providing services to the University of Miami.
- The Laboratory of [name] at the Diabetes Research Institute, University of Miami, Miami, Florida, where samples from patients will be processed, divided in aliquots, frozen as needed for future analysis.

11.2. Preservation of the Integrity of the Study

All presentations and publications using study data must protect the main objectives of the trial. Data integrity will be maintained and the investigators will publish study results and will apply accepted academic policies and regulations governing the publication.

11.3. Participant Reimbursement and Compensation

Participants will not be compensated for visits attended in the study. The supplement(s) during the course of the study will be provided at no charge to the subjects.

12. STUDY TIMELINE

It is anticipated that patient enrollment will occur during the first three years of the trial. All subjects will be followed until one year after initial treatment, with up to one year further follow-up after the treatment period has ended. Study visits will have a window of ± 14 days starting from visit 2.

APPENDIX A: Schedule of Events (SOE)

Visit number	0	1	2	3	4	5 F1	6 F2	7 F3
Days of the trial ¹	-1	1	120	240	360	480	600	720
Months	1	1	4	8	12	16	20	24
Informed Consent	X							
Medical History	X		X	X	X	X	X	X
Physical Exam ²	X		X	X	X	X	X	X
CBC with differential	X	X	X	X	X			
Prothrombin time (PT/PT-INR)	X		X	X	X	X	X	X
Chemistries	X		X	X	X			
Pregnancy test (blood sample) ⁵	X		X	X	X			
Serum for islet autoantibodies	X		X	X	X	X	X	X
Serology	X							
Mechanistic assessments ³		X	X	X	X	X	X	X
Hemoglobin A1c	X		X	X	X	X	X	X
Stimulated C-peptide at 90 min	X				X			X
MMTT 4 hour	X				X			X
Randomization			X					
Diabetes Assessments (insulin adjustment and Hypoglycemia awareness)	X	X	X	X	X	X	X	X
Clarke Score	X				X			X
Dispensing or Administration of Study Drug		X ⁶	X	X				
• Omega-3 Fatty Acids + Vitamin-D OR • Vitamin-D								
Vitamin D levels ⁴	X		X	X	X	X	X	X
AA/EPA Ratio ⁷	X		X	X	X	X	X	X
Counting of Returned Study Drug			X	X	X			
Subject 7-day blood sugar record and hypoglycemia log	X		X	X	X	X	X	X
Concomitant Medication Review	X	X	X	X	X			
Adverse Events Assessment			X	X	X	X	X	X

1. Screening Visit: Screening MMTT must be at least 3 weeks after diagnosis and preferably within one month (37 days) of randomization for recent onset T1D. For established T1D, screening must take place after 180 days of diagnosis.
2. Physical Exam: Routine exam at screening and quarterly.

3. Mechanistic Assessments: includes samples for RNA, plasma, serum, DNA, measures of B and T cell number/function and cytokine profiles. The schedule for these assessments may vary as appropriate. At no time will the blood draw volume exceed what is allowable according to the subject's body weight.
4. Vitamin D levels will be monitored every 4 months or more frequently at the discretion of the investigator in order to adjust dose to achieve target levels.
5. Pregnancy testing will be conducted in females in reproductive age at 4, 8,12 and 16 months study visit.
6. Study drug(s) will be administered within 48hr from baseline visit (visit 1).
7. Dose will be adjusted to maintain a target AA/EPA ratio of 1.5-3.0. AA/EPA ratios will be monitored monthly until achieving target levels and as per protocol or as clinically indicated thereafter.

F1-F3. Follow-Up after 12 Months: Visits will be conducted approximately every 4 months (16, 20, and 24 months).

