	
 Affected by T1D, according to ADA standard criteria, and confirmed by positivity of at least one T1D-associated autoantibody, to GAD65, IA-2, ZnT8, or insulin autoantibody (if patient has been treated with insulin for less than 2 weeks). T1D must be treated with insulin (except if participant is in Honeymoon period/phase). Stimulated C-peptide peak level, at the baseline 1 visit MMTT, ≥ 0.2 ng/ml. Female subjects of childbearing potential must have a negative pregnancy test upon study entry. Adequate venous access to support study required blood draws. 
Exclusion Criteria
 
Patients must not meet any of the following criteria to be eligible to participate:
 
 Inability or unwillingness of a participant to give written informed consent or comply with study protocol. $BMI > 30 \text{ kg/m}^2$. Contra-indications to any of the drugs used in the trial (as per package insert, e.g., knowledge of hypersensitivity to drugs or its excipients). Uncompensated heart failure, fluid overload, myocardial infarction or liver disease or severe impairment of a vital organ within the last 6 weeks before enrollment. Any of the following laboratory findings indicating hemoglobin < 10.0 g/dL; leukocytes $< 3,000/\mu\text{L}$; neutrophils $< 1,500/\mu\text{L}$; lymphocytes $< 800/\mu\text{L}$; platelets $< 100,000/\mu\text{L}$. Any sign or diagnosis of significant chronic active infection (e.g., hepatitis, tuberculosis, EBV, or CMV), or screening laboratory evidence consistent with a significant chronic active infection (such as positive for HIV, IGRA test for TB, or hepatitis B-C). Ongoing acute infections, e.g., acute respiratory tract, urinary tract, or gastrointestinal tract infections. Ongoing or anticipated use of diabetes medications other than insulin. Current or ongoing use of non-insulin pharmaceuticals that affect glycemic control within prior 7 days of screening. Recent recipient of any licensed or investigational live attenuated vaccine(s) within 6 weeks of randomization. Use of investigational drugs within 3 months of participation. Concomitant therapy with immunosuppressive drugs, immunomodulators, or cytotoxic agents, or previous therapy less than 3 months from randomization.

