4.3. Investigational Plan

This is a randomized, open-label, parallel-group, pilot phase I/IIa clinical study. Approximately 56 subjects will be randomly assigned to receive either Omega-3 Fatty Acids and Vitamin D combination or Vitamin D alone. All subjects will be given Vitamin D supplement. Patients to be included in this study are those diagnosed with new onset T1D (diagnosed within the last 180 days) or with established T1D (more than 6 months).

Participation for each subject will last approximately 2 years. Potential participants will have a screening visit to review their overall health, measure diabetes T1D-associated autoantibodies and perform a MMTT, which will also serve as the baseline MMTT. Eligible subjects will be invited to participate in the intervention trial for one year, and then followed for a second year to monitor safety and whether any potential therapeutic benefit, whether metabolic, endocrine, and/or immunological, persists after the therapy has been stopped.

We will evaluate beta cell function by examining C-peptide responses during a MMTT.

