To appropriately gauge the dose of omega 3 fatty acids we are proposing the use of the AA/EPA ratio to guide dosing. As noted above, AA/EPA ratios in the 1.5 to 3.0 range have been studied in healthy volunteers and in children with ADHD have shown an association with clinical outcomes and noted to be safe. Further, such low ratios can be achieved by diet alone as documented in the Japanese population where the average fish consumption has been reported to be one serving of 85 g (3 oz; 900 mg EPA and DHA) per day and 90% of individuals eat fish at least once a week [7].

In view of the chronic nature of the immunopathogenesis of type 1 diabetes it is then not unexpected that therapeutic interventions started at disease onset to preserve beta cell function have usually been administered for a duration of 6 month to 2 years [8-10]. It is important, however, to highlight that one of the main factors responsible for determining the duration of therapy is the safety profile of the proposed intervention.

Data from TrialNet intervention trials has allowed to study the decline in C-peptide 2 years following type 1 diabetes onset which shows a biphasic profile with a steeper decline during the first year [11] suggesting that processes involved with beta-cell loss may be more aggressive during the first year of diagnosis. Thus, therapies aimed to preserve beta-cell function in new onset disease may likely need to be administered over a prolonged period of time and for at least 1 year following disease onset.

In established disease, duration of therapy is also dependent on the mechanism of the intervention and the safety profile. Since inflammation affecting glycemic control may be a chronic state in patients with type 1 diabetes and in view of the reportedly safety profile of high-dose omega 3 fatty acids, we have proposed treating patients with established type 1 diabetes for a duration of 1 year.

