6.8. Visit Windows

The initial study drug administration must begin within 180 days from the day of diagnosis. All subsequent treatment visits and follow up visits in Appendix 1 must occur within the time limits specified below:

The table below depicts summary of visit windows.

Visit Windows	
Visit 0	At least 2 weeks before visit 1
Visit 1	New onset group (randomization \leq 180 days from T1D diagnosis) or established T1D ($>$ 180 days and $<$ 10 years from T1D diagnosis)
Visit 2-4 (Days 120, 240, 360)	\pm 14 days
Follow-up between year 1 and 2	
Every four months	\pm 14 days

During the course of the study, participants who complete one year treatment will receive combination therapy of Omega-3 Fatty Acids and Vitamin D or Vitamin D alone. In addition, participants will frequently undergo assessments of their insulin production, immunological status, and overall health. The participant's insulin production will be measured by a series of MMTTs conducted regularly during the study. The participant's diabetes control will be evaluated by measuring HbA1c every four months and clinical records including insulin types, doses, administration times and blood glucose records.

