9.2. Endpoints/Outcomes

Primary endpoint:

- Stimulated (90 minute sample of a MMTT) C-peptide at the 1 year visit greater or equal to baseline level.

Secondary Objective(s)

- Stimulated C-peptide area under the curve during a 4-hour MMTT greater or equal to baseline level, at the 1 year visit.
- Reduction in HbA1c at the one year visit compared to baseline.
- Reduction in insulin requirement at the 1 year visit compared to baseline.
- Incidence of adverse events (AE) comparable to general diabetes population.

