9.4.3. Supportive Analyses of the Primary Endpoint(s)/Outcome(s)

90-min C-peptide measured at screening and , 12 months and 24 months in the different treatment groups will additionally be fit to a mixed linear regression model, allowing estimation and testing of means and differences between groups at each time point, while simultaneously accommodating the correlation arising from the longitudinal study design in estimates of variances used in tests of significance. We will also estimate and test the differential rate of change in mean 90-min C-peptide over time between these groups, by incorporating an interaction term between time point and treatment group into the models. Although this investigation is not specifically powered to test this interaction, this might provide us with useful insight as to the differences in the effect of combination therapy over time on 90-min C-peptide.

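### The screening MMTT that serves as baseline for the primary endpoint has no binding maximum age at randomization, so C-peptide change before the first dose is scored as change on treatment

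*Combined protocol and SAP*

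**What the plan says.** Section 9.2 defines the primary endpoint as "Stimulated (90 minute sample of a MMTT) C-peptide at the 1 year visit greater or equal to baseline level". It allows no tolerance, so any net fall is a failure.

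Three places identify the baseline test:
- Section 4.3 has the screening visit "perform a MMTT, which will also serve as the baseline MMTT".
- The supportive model in section 9.4.3 uses "90-min C-peptide measured at screening and , 12 months and 24 months".
- The Appendix A grid places the MMTT at visits 0, 4 and 7, with none at visit 1.

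Two places govern its timing:
- The Visit 0 row of section 6.8 reads "At least 2 weeks before visit 1". This is a minimum with no maximum.
- Appendix A, footnote 1, reads "Screening MMTT must be at least 3 weeks after diagnosis and preferably within one month (37 days) of randomization for recent onset T1D". The three weeks are mandatory and the 37 days are preferred. For established T1D the footnote gives only an earliest date, after day 180 from diagnosis.

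Section 4.4.1 allows new-onset randomization up to day 180. I found no rule that requires a repeat MMTT when the first has become old.

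**The concern.** A one-year change score should describe the year on treatment. Here the starting value may be taken months before the first dose, and whatever happens in between is credited to, or charged against, the assigned regimen. The documents give a reason to expect loss in those months: section 5.4.1 describes C-peptide after onset as having a "biphasic profile with a steeper decline during the first year". With a threshold at exactly baseline, a participant whose decline stops completely at the first dose can still be a non-responder because of what was lost earlier.

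At stake are the responder rates in both arms, the power to separate them, and the meaning of the one-year change in the new-onset half of the trial. The secondary AUC endpoint uses the same MMTT and has the same weakness.

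**Working it through.** **The plan's own figure.** Section 9.7 gives 12 per group for 80% power, 5% against 50%. With alpha 0.05 (assumed, since none is stated for the primary test), the pooled formula gives 12 one-sided and 15 two-sided, and the unpooled two-sided formula gives 12. So 12 reproduces. With 28 per arm and 10% attrition, 28 × 0.9 = 25.2, or about 25 evaluable per arm.

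**The permitted gap, new onset.** Earliest MMTT is day 21 and latest randomization is day 180: 180 − 21 = 159 days, or 5.2 months. The nominal span between the two MMTTs is then 159 + 360 = 519 days, of which 360/519 = 69% is on treatment. For established T1D the text yields no comparable ceiling.

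**Illustrative model.** Assumptions not in the documents:
- Annual decline d is 20%, 30% or 45%.
- MMTT test-retest CV is 15%.
- Combination therapy halts decline from the first dose, while control continues to decline.
- The established half follows the same model with a 37-day gap throughout.

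Responder probability = Φ(ln(1 − d) × t/365 ÷ (√2 × 0.15)). Here t is the gap for the combination arm, and the gap plus 360 days for control.

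Worked case, d = 30%, √2 × 0.15 = 0.212:
- Combination, 159 days: −0.357 × 159/365 = −0.155; −0.155/0.212 = −0.73; Φ = 0.232.
- Combination, 37 days: Φ = 0.432.
- Control, 519 days: 0.008. Control, 397 days: 0.034.
- Half the arm at each gap: combination (0.232 + 0.432)/2 = 0.332; control (0.008 + 0.034)/2 = 0.021.
- Two-sided pooled test, 25 per arm: mean rate 0.1765; Φ[(0.311 × 5 − 1.96 × 0.539)/0.492] = Φ(1.01) = 0.84. With 37 days for everyone the same formula gives 0.94.

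All three decline rates, power at 25 per arm:

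| Annual decline | 37 days for all | New-onset half at 159 days | Loss |
|---|---|---|---|
| 20% | 75% | 69% | 6 points |
| 30% | 94% | 84% | 10 points |
| 45% | 96% | 77% | 18 points |

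Moving the new-onset half from 37 to 90 days costs about 2 to 7 points.

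**Sensitivity to the power calculation.** These figures use the normal-approximation formula. Enumerating the binomial outcomes for the same uncorrected test gives 77% to 72%, 97% to 92% and 99.6% to 90%, so losses of about 5 to 10 points.

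**Cross-check with the plan's own rates.** Take a normal model in which 5% and 50% fix the arm means, and let the gap run at the implied control rate. With only the new-onset half at 159 days and the others at no gap, the rates become 2.9% and 36.7% and power is 87%. It is 96% with that half at 37 days and 97% with no gap at all.

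**The case against.** The strongest reply is that 159 days is a corner case. It needs an MMTT on exactly day 21 and randomization on exactly day 180, while the footnote's stated preference is 37 days. Nothing in the documents says long gaps are expected, and no distribution of gaps is given. This stands, and it is why the 90-day figures matter as much as the extreme.

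The decline itself is also uncertain. The plan contrasts the first year with the second. It does not claim a constant fall between day 21 and day 180, and it recognises a honeymoon phase in these patients. This stands too. If C-peptide is stable before dosing nothing is lost, and if it rises an old baseline creates responders the treatment did not produce.

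Other parts of the analysis help, but only partly. The mixed model in section 9.4.3 compares arm means at each time point, so loss common to both arms does not become failure there. The adjusted logistic model in section 9.4.2 includes time since diagnosis, which limits how long a new-onset gap can be, but not the gap itself. Neither repairs the binary primary endpoint.

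A reader might infer three stronger things:
- That the gap biases the comparison or inflates type I error. It arises before randomization, which is stratified by new versus established disease, so it is expected to be equal in both arms. Chance imbalance is possible at 28 per arm.
- That five months is the ceiling for everyone. It derives from new-onset limits only, and the steeper-decline statement does not cover disease of up to ten years.
- That the protocol already has a 37-day standard for established T1D. Footnote 1 gives that figure for recent onset only.

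**Conclusion.** The baseline for the primary endpoint has no binding maximum age, and no other provision corrects this for the responder definition. The consequence is lower responder rates in both arms, lower power, and a nominal one-year change that can span 519 days in new-onset participants.

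The size is moderate: about 6 to 18 points of power by the standard formula (5 to 10 by enumeration) if every new-onset participant sat at the extreme gap, and zero if C-peptide is stable before dosing. These figures rest on assumed decline rates, an assumed CV, a two-sided alpha of 0.05 and full halting of decline by the combination. The absence of a binding limit rests on the text alone. This is a cheap improvement to the plan, not a threat to its validity.

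**What to change.** **Main change.**
- In Appendix A, footnote 1, remove the word *preferably* so that 37 days binds for new-onset participants.
- Add the same maximum to the Visit 0 row of section 6.8.
- Have the sponsor choose and justify its own maximum for established T1D.
- In section 9.4, add a sensitivity analysis of the primary endpoint adjusting for the interval from MMTT to randomization.

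**Cost.** Visit 1 must be scheduled more tightly, and an occasional late participant will be rescheduled or retested. Retesting is an extra procedure (38.5 mL) and should not be the main remedy. If it is allowed, the plan should state which MMTT is the baseline and how a repeat peak below the 0.2 ng/ml entry threshold is handled. Sample size does not change.

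**Separately, reconcile three contradictions.**
- The synopsis refers to "Stimulated C-peptide peak level, at the baseline 1 visit MMTT", but no MMTT is scheduled at visit 1.
- Appendix A heads visit 0 as day −1, but section 6.8 requires at least two weeks before visit 1.
- Section 6.8 states without group restriction: "The initial study drug administration must begin within 180 days from the day of diagnosis". Read literally this would bar Groups I and III (28 of 56 participants). That reading is not supported as intent, because the Visit 1 row below it and section 4.4.1 admit established T1D, but the passages must agree.
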